### 10.2.2 Description of Treatment Toxicities

Toxicities will be tabulated by CTCAE grade and type.

### 10.2.3 Correlative Laboratory Studies

Biochemical and genomic measurements will be summarized both graphically and numerically using descriptive statistics. Transformations will be performed based on the observed distribution of the endpoints. Cox regression will be used to estimate hazard ratios measuring the association between these measures and RFS. 95% confidence will be estimated for the hazard ratios as appropriate.

For the amount of antibody forcement antigen, graphical displays such as scatterplots of optical density of particular color and dilution will be made for pre- and post-vaccination. To investigate if the distributions of pre- and post-vaccination are different, Kolmogorov-Smirnov test will be performed. The reverse sigmoidal curves will fit to estimate model parameters such as slope and 50% of maximum effect for the antibody measurement. Depending on the curve results, different percentages of maximum effect (e.g., 65-75%) will be investigated as well. Moreover, those interest of immune parameters will be compared between pre- and post-vaccination. The

difference of the immune parameters will be used for measuring the association between these measures and time to relapse/stress.

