## **2.6 BACKGROUND FOR STUDY OF SOCIOBIOLOGICAL RESPONSES TO STRESS IN PROSTATE CANCER**

### **2.6.1 Biological Pathways to Racial Disparities in Prostate Cancer Outcomes**

Despite increased access to early detection and the availability of more effective therapeutic strategies, African Americans with prostate cancer continue to experience excess rates of morbidity and mortality from this disease. A vast array of genomic and epigenomic studies of prostate cancer cells, or peri-tumoral stroma, have identified differences among racial groups. An emerging hypothesis about prostate cancer disparities is that social conditions and physiological responses to social stressors influence biological processes, and are important to the aggressive behavior, and poor response to treatment, among African Americans (81). This hypothesis is supported by animal studies showing that chronic stress promotes tumor development and progression in various rodent cancer models (82,83) including prostate cancer models (84). Chronic stress has also been shown to augment the normal age-related senescence of the immune system, enhancing the low of T cell diversity and increasing systemic inflammation (85,86).

The mechanisms through which socio-economic stressors affect several and varied phenotypes in cancer patients are not clear. The postulated mechanisms derive from the HPA axis (1) or the SNS (87) in most studies. In the former case, chronically elevated cortisol has been identified as

a mediator of stress, acting through the polymorphic GR. In the latter case, norepinephrine is thought to regulate VEGF- and PKA-dependent signaling pathways, leading to increased proliferation and migration. Recent work has also implicated stress-induced loss of *TP53* function (88). These pathways are not mutually exclusive, and multiple signaling events may be involved in mediating stress effects.

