The optional sub-study will involve correlative analyses will demonstrate another distinct feature by studying the pathways within the setting of a clinical trial of prostate cancer immunotherapy. The clinical trial itself was designed and powered to detect a therapeutic effect in prostate cancer patients. It is not a trial designed to measure an irrelevant immune response in normal volunteers or non-cancer patients. Hence, the psychologic insights will be derived from, and applicable to, a “real world” setting. The PROSTVAC vaccine has been in development for several years, and randomized Phase II trials in patients with advanced disease have shown an improvement in overall survival. The PROSPECT trial, designated by the FDA as the registration trial, completed worldwide accrual in December, 2014. Interim analyses will be made in early 2017, with the hope for FDA approval in late 2017 or early 2018. The present trial focuses on a different population, a minimally-treated population after prostatectomy. The physiologic, and likely psychologic, conditions of these subjects are markedly different from those in the PROSPECT trial. MUSC investigators will make comparisons between measurement of SR and other psychologic parameters, and clinical (relapse-free survival), genomic (IgG allotypes), and immunologic (anti-Forssman antibody, antigen-restricted effector T cell populations) measurements. Thus, if the vaccine turns out not to have the desired clinical effect, the investigators will still be able to examine the relationship between stress and immune response development.

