### 4.2 PATIENT POPULATION

This study will be conducted at MUSC and the VAMC. There are approximately 80 radical prostatectomies performed yearly at MUSC (30% African American), and 70 at the VAMC (70% African American). Both institutions have extensive experience with prostate cancer clinical trials, and investigators have been particularly successful in recruiting African American subjects. Therapeutic trial accruals in the HCC include approximately 25% African American subjects, reflecting a close match to the 30% prevalence of African Americans in the population of South Carolina. This study will aim to enroll equal numbers of African American and Caucasian subjects.

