### 8.1.3 Measurement of IgG Allotypes GM and KM

Polymorphic hereditary antigenic determinants present on IgG heavy chains are called GM allotypes (33, 34). These determinants are inherited as autosomal codominant genes according to Mendelian laws. They are encoded by three very closely linked genes—immunoglobulin heavy chain G1 (IGHG1), IGHG2, and IGHG3—on chromosome 14q32. GM alleles are expressed on the constant region of Y1, Y2, and Y3 chains. There are currently 18 serologically testable GM specificities—four on Y1 (1/a, 2/x, 3/f, 17/z), one on Y2 (23/n), and 13 on Y3 (5/b1, 6/c3, 10/b5, 11/b0, 13/b3, 14/b4, 15/s, 16/t, 21/g1, 24/c5, 26/u, 27/v, 28/g5). Linkage disequilibrium in the GM gene complex within a racial group is almost absolute and the determinants are transmitted as a group—haplotypes.

Polymorphic hereditary antigenic determinants present on Y-type light chains are called KM allotypes. Three alleles—KM 1, KM 1,2, and KM 3—segregate at the immunoglobulin Y constant (IGKC) locus on chromosome 2p12. KM 1 allele, without KM 2, is rare; 98% of the individuals positive for KM 1 are also positive for KM 2. Thus, positivity for KM 1 includes both KM 1 and KM 1,2 alleles (33,34).

Immunoglobulin GM genes are one of the most powerful tools for genetic characterization of human populations. For instance, unless there is genetic admixture, GM 3 is not found in African Americans; GM 6 is present only in people of African ancestry; GM 1 is polymorphic only in people of European ancestry. Their racially associated prevalence makes them especially suitable for investigations involving racial disparity in prostate cancer. Furthermore, these markers have been shown to contribute to both cellular and humoral immunity to several tumor-associated antigens in a racially restricted manner ((105-112)(113-115)). Thus, this project could potentially identify racially-specific genetic correlates of PROSTVAC vaccine efficacy. Immunoglobulin GM and KM genotyping may provide an import co-variant to measure along with stress responses. Because of almost absolute linkage disequilibrium between particular GM allotypes within a race, not all markers need to be typed to determine the major haplotypes segregating in a population.

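### Section 10.2.3 names no handling of race for GM 3 and GM 6, which the protocol says track race, so their pooled RFS hazard ratios would be confounded if race is related to relapse

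*Combined protocol and SAP*

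**What the plan says.** Section 10.2.3 covers the biochemical and genomic markers in one sentence: "Cox regression will be used to estimate hazard ratios measuring the association between these measures and RFS". It adds 95% intervals for the hazard ratios and says nothing about covariates, strata or subgroups. The synopsis repeats the plan in the same terms. Section 2.6.2 classes IgG allotypes as genomic measurements, so they fall under this sentence. Section 3.2 makes the matching secondary objective a descriptive one.

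Section 8.1.3 describes how the GM markers are distributed: "unless there is genetic admixture, GM 3 is not found in African Americans; GM 6 is present only in people of African ancestry", and "GM 1 is polymorphic only in people of European ancestry". It adds that "Linkage disequilibrium in the GM gene complex within a racial group is almost absolute". It gives the purpose of the typing as follows: "this project could potentially identify racially-specific genetic correlates of PROSTVAC vaccine efficacy".

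On race more generally:
- Section 4.2: "This study will aim to enroll equal numbers of African American and Caucasian subjects".
- Section 2.6.1: "African Americans with prostate cancer continue to experience excess rates of morbidity and mortality from this disease".
- Section 3.2 matches the institutional historical comparison group on race before comparing RFS.
- Section 10.3 compares RFS between racial groups by log-rank test and leaves a Cox model to be explored. Its one adjusted model, a logistic regression of immune response on stress reactivity, gives age and perceived stress as example covariates and does not list race.
- Section 10.5 lists race among the parameters recorded for each man.

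**The concern.** A hazard ratio for an allotype is meant to describe the allotype. In a cohort that is half African American and half Caucasian, men who carry GM 6 are all of African ancestry, and men who carry GM 3 are almost all not African American. Comparing carriers with non-carriers across the whole cohort therefore also compares two different racial mixes. If relapse risk differs by race for any reason, part of that difference is attributed to the marker.

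The protocol treats race as relevant to RFS in its background, in the matching of historical controls and in the sub-study. It does not do so in the models whose markers it describes as most closely tied to race. Section 8.1.3 looks for race-specific genetic correlates of vaccine efficacy, but no section specifies an analysis within race. A racial difference in relapse could then be reported as a genetic finding.

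**Working it through.** **The plan's own figure.** There is none to reproduce. No sample size, power or significance level is given for the allotype analyses.

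**Inputs from the documents.** 30 evaluable men (synopsis and Section 10.1; Section 4.1 still says 40), 1:1 by race (Section 4.2), so 15 and 15. The 2-year RFS is 0.60 (Section 10.1), so expected events are 30 × 0.40 = 12. At the target RFS of 0.78 they would be 30 × 0.22 = 6.6.

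**Assumed inputs, shown as ranges.** The documents give no race hazard ratio and no carriage frequency. Race hazard ratios (African American versus Caucasian) of 1, 1.5, 2 and 3 were used, with several carriage patterns. The allotype effect is zero throughout.

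**Step 1: apparent hazard ratio.** At the start of follow-up it is the ratio of the average hazards of carriers and non-carriers. Let carriage be c in African American men and 0 in Caucasian men, with race hazard ratio R. Carriers have hazard R. Non-carriers have average hazard [0.5 + 0.5(1 − c)R] / [0.5 + 0.5(1 − c)].

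- c = 0.7, R = 2: non-carriers (0.5 + 0.15 × 2)/0.65 = 1.23; ratio 2/1.23 = 1.63.
- c = 0.4, R = 2: non-carriers (0.5 + 0.30 × 2)/0.80 = 1.375; ratio 2/1.375 = 1.45.
- c = 0.7, R = 1.5: non-carriers (0.5 + 0.225)/0.65 = 1.115; ratio 1.5/1.115 = 1.34.
- c = 0.4, R = 1.5: non-carriers (0.5 + 0.45)/0.80 = 1.1875; ratio 1.5/1.1875 = 1.26.

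Cox fits to 200,000 simulated men followed for two years give 1.65, 1.50, 1.35 and 1.27 in the same order. For a GM 3-like marker (5% of African American and 80% of Caucasian men) the fits give 0.74 at R = 1.5 and 0.58 at R = 2.

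**Step 2: how often a null marker looks positive.** The settings were 30 men, exponential RFS with overall 2-year RFS 0.60, follow-up to 2 years and 6,000 runs per cell. The test was the two-sided 5% Cox score (log-rank) test, used as a stand-in for a 95% interval excluding 1.

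| Carriage, African American / Caucasian | Pooled, R = 1 | R = 1.5 | R = 2 | R = 3 | Stratified by race, all R |
|---|---|---|---|---|---|
| 0.4 / 0 | 0.06 | 0.09 | 0.13 | 0.21 | 0.05–0.06 |
| 0.7 / 0 | 0.05 | 0.10 | 0.16 | 0.30 | 0.06–0.07 |
| 0.05 / 0.8 | 0.05 | 0.08 | 0.14 | 0.27 | 0.06–0.07 |
| 1.0 / 0 | 0.05 | 0.11 | 0.22 | 0.45 | not estimable |
| 0.5 / 0.5 | 0.05 | 0.05 | 0.06 | 0.05 | 0.05–0.06 |

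The inflation needs both a race-linked marker and a race effect. Stratification removes nearly all of it where the marker varies within race. Where carriage is all-or-none, the stratified test has no information.

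**Step 3: what the within-race estimate costs.** If 12 events split evenly, each race has about 6. For 50% carriage within one race, the standard error of the log hazard ratio is about √(4/6) = 0.82. The 95% interval then extends by a factor of exp(1.96 × 0.82) ≈ 5 each way.

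For a GM 3-like allele carried by 90% of 15 Caucasian men, with RFS 0.60 in that group, the chance of having no non-carrier is 0.9^15 = 21%. The chance that non-carriers contribute no event is (1 − 0.1 × 0.4)^15 = 54%. At 80% carriage the latter is (1 − 0.2 × 0.4)^15 = 29%.

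**The case against.** Much of the case for the plan stands, and it limits the point.

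- A reader might infer that the plan prescribes unadjusted models. It does not. Section 10.2.3 neither lists nor rules out covariates. The gap is one of silence, which leaves the handling of race to be settled after the data are seen.
- A reader might infer that an allotype analysis would simply be a test of race. That holds only if carriage is all-or-none by race. Section 8.1.3 says where GM 6 occurs, not that every man of African ancestry carries it. With partial carriage the result is partly confounded, and with no race effect on RFS it is not confounded at all.
- The objective is descriptive, with intervals and no decision rule, so the rejection rates only indicate how often an interval would mislead. The bias in the hazard ratio remains: the interval would be centred on the wrong value.
- The race effect is weakly sourced. Section 2.6.1 concerns prostate cancer in general, not RFS after prostatectomy in high-risk men.
- The scope is narrow. Section 8.1.3 describes a race-specific distribution for GM 3, GM 6 and, less strictly, GM 1. The documents do not describe KM, FcR, TSC22D3 or glucocorticoid-receptor variants as race-exclusive. Section 10.2.3 also writes no model of immune response on allotype, so the point does not extend to one.
- Section 10.3 will show RFS by race, so a reader could see a racial difference alongside the marker result. That does not correct the marker estimate.
- Stratification has a real cost, as step 3 shows: the within-race hazard ratio may often be infinite or undefined.

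**Conclusion.** The point holds for GM 3 and GM 6 in the RFS models. Pooled as Section 10.2.3 is written, their hazard ratios would be confounded by race if race is related to RFS. With carriage of 40–70% in African American men and none in Caucasian men, a null allotype would show an apparent hazard ratio of about 1.27–1.35 at a race hazard ratio of 1.5, and 1.50–1.65 at 2. A nominal 5% test would reject in about 9–10% and 13–16% of trials respectively, and in about 5–6% when race has no effect. These sizes rest on assumed race hazard ratios and carriage rates, a 1:1 racial mix, 30 men and 2-year RFS of 0.60. The direction of the problem rests only on what the protocol says about the markers and about race. It concerns a descriptive secondary analysis of about 12 events and does not touch the primary conclusion.

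**What to change.** In Section 10.2.3, state in advance that:

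1. Cox models of GM allotypes on RFS are stratified by race.
2. An allele confined to one race is analysed within that race.
3. A marker with no within-race variation, or with too few events to estimate a hazard ratio, is reported as inseparable from race.
4. Any pooled estimate is labelled as descriptive and confounded by race.

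The same stratification may be applied to the other genotype models as a precaution, though the documents do not show that they need it.

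The change is one of wording. Race is already recorded under Section 10.5, so no new data, visits or patients are required. The price is precision: within-race intervals will be wide and some hazard ratios will not be estimable, more so if events fall towards the 6.6 expected at the target RFS. Recorded race is also an imperfect stand-in for ancestry, given the protocol's own caveat about admixture, so some confounding may remain within strata.

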## 7.5 EFFICACY ASSESSMENTS

Efficacy assessments will primarily be performed by measurement of PSA and by physical assessment. Imaging studies (CT scans of the abdomen and pelvis, and bone scans) will be performed at baseline (up to 16 weeks prior to treatment) and at the end of the study (or within the preceding 2 months before end of study). Otherwise, scans will be performed only if clinically indicated for evaluation of relapse or off study. Additional forms of imaging (Prostascint scan, MRI) may be substituted for a CT scan of the abdomen and pelvis if clinically indicated. However, the imaging method used at baseline will be used for follow up scans. Compliance with therapy may be considered a component of the efficacy assessment. Compliance with PROSTVAC-V/F will be monitored at each visit by interviewing the patient and reviewing the infusion center records for administration.

Both primary and secondary efficacy assessment involve measurement of RFS. Recurrence will be defined as the occurrence of any of the following:

- Institution of new prostate cancer therapy
- First detection of a PSA level  $\geq 0.2$  ng/mL (confirmed  $> 30$  days later) after completion of all PROSTVAC V/F vaccine doses
- Development of radiographically-demonstrable metastases
- Death

RFS at two years will be met if a patient has met none of the above criteria two years post-surgery. RFS as a time to event endpoint will be measured as the time in days from surgery to any of the above conditions being met.

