## 8 CORRELATIVE STUDIES

### 8.1 RESEARCH BLOOD COLLECTIONS

A variety of analyses will be performed on the research blood samples collected for this study. To evaluate biological responses to vaccinations, plasma, serum, as well as whole blood samples will be collected from all enrolled subjects. Plasma will be analyzed for the development of antibodies to the vaccinia and fowlpox virus vectors, the PSA insert, other prostate specific antigens, as well as tumor associated antigens. Serum will also be profiled for changes in cytokine and chemokine expression and circulating tumor markers. Immune function analysis will be performed by isolation of PBMCs for immune function assays. PBMCs will be evaluated for PSA antigen-specific responses by ELISPOT and flow cytometric-based methods. Determinant spreading to other prostate antigens and tumor-associated antigens will also be examined. All evaluations will be performed at laboratories using standardized procedures. Subject samples may be kept for up to one year past the end of the trial for assay development, implementation, and data review. These described analyses will generate a large dataset that will potentially enable the identification of new biomarkers of disease prognosis and/or vaccine response.

Research assessments will not be made in real time, since they will require analyses that will be performed only in “batch mode” when samples are available. Research samples will be collected as indicated and stored for future assays, in accordance with MUSC and VAMC policies.

All patients will be expected to provide blood for research purposes per the timepoints outlined within the study calendar (Appendix A). Each research blood collection will require 38mL of anticoagulated peripheral whole blood.

Research Blood Collection Timepoints	At each blood collection, collect the following	
	Amount of Blood	Tube type
Baseline Day 85 Day 225 Day 730 or off study	10 mL	sodium heparin tube
	7 mL	lithium heparin tube
	21 mL (three 7 mL tubes)	EDTA tube
	7mL	Blood (clot) tube

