#### 8.1.1 Measurement of Antigen-Specific T-Cell Functions

Peripheral blood samples will be collected in EDTA vacutainer tubes prior to vaccination, one week after the third immunization, and one week following final PROSTVAC administration. Red blood cells will be lysed with ACK buffer for isolation of peripheral blood leukocytes (PBL). PBLs will be frozen in 90% FBS/10% DMSO using a controlled-rate freezer, and immediately stored in liquid nitrogen. Phenotypic characterization and detection of prostate specific antigen (PSA)-specific cytokine production from T cells within previously cryopreserved PBL will be performed

simultaneously. Briefly, PBLs will be stimulated at  $5 \times 10^6$  cells per test with peptide pools consisting of sequential 15mer peptides overlapping by 11 amino acids spanning the complete human PSA protein at 1 $\mu$ g/ml/peptide (Miltenyi), 1% DMSO negative control or polyclonal activation via 50 ng/mL phorbol myristate acetate (PMA) and 1  $\mu$ g/ml ionomycin for 6 hours. Brefeldin A (10 mg/mL) will be present for the last 5 hours. Samples will be labeled to exclude dead cells by incubation with amine reactive UV Live/Dead dye (Molecular Probes). Subsequently, T cell memory subsets will be phenotyped by staining for surface antigens using monoclonal antibodies specific for CD3, CD4, CD8, CD45RA, CD45RO, CCR7 and CD64L allowing for detection of naïve, stem cell memory, central memory, effector memory and terminally differentiated effector CD4 $^+$  and CD8 $^+$  T cells. Cells are then fixed and permeabilized by treatment with BD Cytofix/Cytoperm solution (BD Pharmingen) followed by labeling with monoclonal antibodies specific for IFN- $\gamma$ , IL-17A, IL-4, and IL-10 for 30 min at 4 $^{\circ}$ C in the presence of permeabilizing staining buffer to identify predominant TH1, TH17, TH2 and Treg cytokines, respectively. Cells will be collected immediately on a BD Fortessa X-20 flow cytometer capable of detection of up to 18 parameters (Beckman Dickinson). At least 300,000 events will be collected and data analyzed using FlowJo software. Values 3-fold higher than the DMSO background are scored as positive.

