### 8.1.2 Measurement of Anti-Forssman Antibodies

Antibodies to heterophile antigens such as the glycolipid Forssman antigen commonly develop during certain infections. A recent report documented the appearance of antibodies to Forssman antigen during treatment of prostate cancer patients with PROSTVAC (32). Antibodies appeared in a high proportion of subjects (64%) and in high titer. Moreover, the appearance of anti-Forssman antibodies correlated with overall survival after vaccination, and the antibody titer was directly proportional to length of survival. The appearance of anti-Forssman antibodies during PROSTVAC therapy may represent a generalized activation of the immune system, or possibly antigen spreading. Project investigators will use a competitive immunoassay to detect anti-Forssman antibodies in serum from trial subjects before treatment, after the third injection, and after the final injection. Sheep RBCs will be purchased from commercial sources and used as a source of Forssman antigen. Washed RBCs will be incubated with serial dilutions of patient plasma, and with a FITC-labelled anti-Forssman monoclonal antibody. Binding of the labelled antibody will be measured by flow cytometry. Increasing amounts of anti-Forssman antibody in patient plasma will compete with the labelled antibody and reduce its binding, leading to decreased signal in the flow histogram. The amount of bound, labelled antibody will be quantified as the difference in maximum fluorescence intensity of the histogram curves, with irrelevant, isotype-matched antibody as a negative control, and labelled anti-Forssman antibody only (no competitor) as the positive controls. The result will be expressed as serum titer that inhibits binding of the labelled antibody probe by 90%.

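### Section 10.2.3 relates immune change to RFS from surgery without naming the post-vaccination sample or protecting time order, so a Day 225 or off-study sample could coincide with or follow relapse

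*Combined protocol and SAP*

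**What the plan says.** **Analysis.** Section 10.2.3 (Correlative Laboratory Studies) states, for biochemical and genomic measurements, that "Cox regression will be used to estimate hazard ratios measuring the association between these measures and RFS". It then says of the immune parameters that the pre/post "difference of the immune parameters will be used for measuring the association between these measures and time to relapse/stress". It does not say which post-vaccination sample supplies the second value, or how a covariate measured after time zero is handled.

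**Clock and event.** Section 7.5: "RFS as a time to event endpoint will be measured as the time in days from surgery". A PSA relapse is dated at first detection, needs confirmation more than 30 days later, and counts only "after completion of all PROSTVAC V/F vaccine doses". The last dose is on Day 141 (Section 5.2.1), and the next visit column in Appendix A is Day 225.

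**Samples.** The Section 8.1 table lists research blood at "Baseline Day 85 Day 225 Day 730 or off study". Section 8.1.1 places the T-cell samples "prior to vaccination, one week after the third immunization, and one week following final PROSTVAC administration". Section 8.1.2 places the anti-Forssman samples "before treatment, after the third injection, and after the final injection".

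**Going off study.** Section 4.7 lists relapse after completion of dosing as a reason for withdrawal, and Section 7.3 includes research blood among the off-study assessments.

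**The concern.** An immune correlate of relapse can be read as predictive only if the marker was measured before the relapse. Two of the listed post-vaccination samples do not guarantee that.

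- **Day 225.** A PSA rise during dosing is not countable until dosing ends. The next scheduled visit is Day 225, so the relapse would usually be dated at about the visit at which the blood is drawn.
- **Off study.** For a man who relapses, this sample is drawn because he relapsed. For a man who does not, it is drawn at Day 730. The sampling time then depends on the outcome.

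PSA is the vaccine's target antigen, so a rising PSA could plausibly change PSA-specific immunity. A hazard ratio from such samples would mix an effect of immunity on relapse with an effect of relapse on immunity. The association of RFS with immunologic parameters is a listed secondary objective (Section 3.2). Section 8.1.1 hopes to identify immune correlates of protection from progression. Section 2.6.2 relies on the immune measurements if the vaccine shows no clinical effect.

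**Working it through.** **1. The plan's own figures.** The documents give no share of relapses by Day 225. The event counts come from the design in Section 10.1, which reproduces: stopping at 11 or fewer of 19 and rejecting at 22 or more of 30 gives exact type I error 0.093 and power 0.801. The null of 0.60 is close to the simple mean of the two historical values, (0.645 + 0.56)/2 = 0.6025. Expected relapses in 30 men are 30 × 0.40 = 12 under the null and 30 × 0.22 = 6.6 under the alternative.

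**2. Inputs.**
- Database (n = 243): RFS 0.751 at 1 year and 0.645 at 2 years (Section 10.1).
- E3886 (n = 98): 0.73 and 0.56 (Section 10.1).
- Latest treatment start: 120 days after surgery (Section 5.1).
- Earliest start: 45 days after surgery. This is an assumption, suggested by the post-operative PSA timing in Section 7.1.
- Men are relapse-free at Day 1, because PSA must be below 0.2 ng/mL (Section 4.3; Appendix A, footnote m).

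**3. Formula.** Assume constant hazard within each year, so that S(t) = S1^(t/365) in year 1. With start s days after surgery, Day 225 is post-operative day s + 224. The share of post-start two-year relapses at or before Day 225 is

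[S(s) − S(s+224)] / [S(s) − S(730)].

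| Source | s | S(s) | S(s+224) | S(730) | Share |
|---|---|---|---|---|---|
| Database | 45 | 0.965 | 0.810 | 0.645 | 0.49 |
| Database | 120 | 0.910 | 0.764 | 0.645 | 0.55 |
| E3886 | 45 | 0.962 | 0.793 | 0.560 | 0.42 |
| E3886 | 120 | 0.902 | 0.743 | 0.560 | 0.46 |

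**4. Sensitivity.**
- Start at 30 days: 0.47 (database) and 0.41 (E3886).
- One constant hazard over both years, start 45-120 days: 0.37-0.42.
- Averaged curve (0.7405, 0.6025): 0.45-0.50.
- Averaged curve scaled by proportional hazards to a two-year RFS of 0.78: 0.42-0.48.

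**5. Events.** Under the null, 12 × 0.449 to 12 × 0.503 = 5.4 to 6.0. Under the alternative, 6.6 × 0.420 to 6.6 × 0.477 = 2.8 to 3.1. That is about 3-6 of 7-12.

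**6. The other samples.**
- *Day 85* is before Day 141, so it precedes every countable PSA relapse in a man who receives all doses. On the same curves, 17-22% of post-start relapses would already have begun by then, though not yet countable (16% on E3886 if treatment starts at 30 days).
- *One week after the last dose* (141 + 7 = Day 148, as Section 8.1.1 implies) would precede nearly all countable PSA relapses.
- *Off study* follows the relapse by construction, since a PSA relapse is dated at first detection and confirmed more than 30 days later.

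**7. Conflicting timings.** Section 8.1.1 implies draws about a week after the third dose and at about Day 148. Section 8.1 has Day 85 (the day of the fifth dose) and Day 225. Section 8.1.2 gives no days. An analyst could therefore choose the sample after seeing the data.

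**The case against.** **The plan never says that Day 225 or the off-study sample is the exposure.** This is correct, and it limits the point. A reader might infer that the marker is generally measured at or after relapse. The documents do not support that: Day 85 is also a post-vaccination sample, and a draw one week after the last dose would be nearly as safe for countable PSA relapses. Even at Day 225, most early relapses would coincide with the sample and few would precede it.

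**The share may be too high.** This stands. The database admitted men with persistently detectable PSA after surgery (Section 10.1), and 17% of the E3886 men had detectable post-operative PSA (Appendix B), whereas this trial requires PSA below 0.2 ng/mL. A reader might also quote the database alone for a figure above one half; E3886, the plan's other source, gives 41-46%.

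**Day 85 is not a complete cure.** This also stands. Some men would have PSA already rising at Day 85 but not yet countable, and that sample cannot reflect the later doses. The documents give no ground for making it the main exposure.

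**The analysis is descriptive, and the sentence on the difference names no model.** Both are true. Cox regression is named two sentences groups earlier, for biochemical and genomic measures, so its use for the immune difference is an inference. Any time-to-relapse analysis of that difference would nevertheless need the same time ordering.

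**Conclusion.** The concern holds in a limited form. The plan relates a covariate measured after treatment starts to RFS counted from surgery, names no sample, and states no method that keeps the marker ahead of the event. With Day 225 as the exposure, roughly 40-55% of post-start two-year relapses, about 3-6 of 7-12, would be dated at or about the same visit. With the off-study sample as the exposure, the marker in relapsers is triggered by the event; that conclusion needs no assumption about rates. Day 85 is free of the problem for countable PSA relapses in fully dosed men. Relapse by metastasis, new therapy or death can count earlier.

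The size rests on historical rates carried over to this population, a piecewise-constant hazard and starts 30-120 days after surgery; a single constant hazard gives 37-42%. The Appendix A grid was incomplete in the copy read, so the PSA marks at each visit could not be checked, although footnote p requires at least a PSA at follow-up visits.

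A reader might infer that the immune-correlate objective cannot be met at all, or that the efficacy conclusion is affected. Neither follows: a suitable sample exists, and the primary test does not use these data. This is an inexpensive improvement to a secondary, exploratory analysis.

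**What to change.** Amend Section 10.2.3 and reconcile the sampling text:

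1. Name the post-vaccination sample used for each assay, and make Sections 8.1, 8.1.1 and 8.1.2 agree on when it is drawn.
2. For each sample used as an exposure, include only men who are event-free on that sample date, treating a first PSA detection at that visit as an event, and count only later relapses (a landmark analysis). Alternatively, use a time-dependent covariate with delayed entry.
3. State that off-study samples are not used as an exposure.
4. Add a sensitivity analysis excluding men whose PSA is already 0.2 ng/mL or higher at the landmark, whether or not it yet counts as relapse.

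**Cost.** The change is to wording; if the reconciled timings differ from current practice, the sampling schedule must follow. A Day 225 landmark keeps about 45-58% of the relapses: about 5-7 of 12, or 3-4 of 6.6. From exp[(1.96 + 0.84)/√d], with d events, 80% power at two-sided 0.05 needs a hazard ratio of about 3.1 per standard deviation of a continuous marker with 6 events, against about 2.2 with all 12. A Day 85 landmark loses almost no events but does not reflect the response to the later doses. The choice between them belongs to the investigators and should be made before the assay data are seen.
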